#### **10.4.1.1 Summary Statistics**

For each vital signs variable at each visit the assessments will be summarized by treatment arm. The summary includes descriptive statistics such as the number of subjects with data, mean (standard deviation), median, minimum, and maximum values, for observed values and change from baseline at each time-point for each vital signs variable. Change from baseline values will not be summarized for orthostatic vital signs.

#### **10.4.1.2 Data Listings**

Data listings will be prepared by site for all subjects with any abnormal or markedly abnormal vital signs value at any time-point (including screening, baseline). The pre-specified markedly abnormal criteria are presented in [Appendix 1](#).

Data listing of orthostatic vital signs will also be prepared by site for all subjects with any orthostatic vital signs values that are indicative of fluid volume depletion at any time-point.

#### **10.4.2 ECGs**

Overall ECG assessment will be categorized as 'normal', 'abnormal, not clinically significant', or 'abnormal, clinically significant' (as judged by the Investigator). These categorized values will be summarized by treatment for each assessment time for the safety population.

QTc will be calculated both using Bazett's and Fridericia's correction formulae (see below for definitions).

---

1) Bazett's correction (square root):

$$QTcB = QT / (RR)^{0.5}$$

2) Fridericia's correction (cube root):

$$QTcF = QT / (RR)^{1/3}$$

where RR is in sec (=1 for HR=60 bpm), whereas QT is in msec.

#### **10.4.2.1 Summary Statistics**

For the ECG parameters PR, QRS and QTc, descriptive statistics, i.e., the number of subjects with data, mean (standard deviation), median, minimum, and maximum values, will be presented for observed values and change from baseline at each time-point and for the last assessment in the study

#### **10.4.2.2 Data Listings**

Data listings will be prepared by treatment group and centre for all subjects with any abnormal ECG or markedly abnormal value at any time-point, including screening, baseline, during treatment, and post-treatment. The pre-specified markedly abnormal criteria are presented in [Appendix 1](#) .

### **10.5 Other Safety Variables**

The total fluid intake collected on patient diary will be summarized by treatment group. The summary will by each type liquid intake specified in the patient dairy. Associated listing will also be produced. The listing will include information on the time and type of liquid consumed from the start of the first dose of IMP to the time of colonoscopy. A separate listing will be produced for the volume of liquid used at time of procedure (including fluid IV).

## **11 Interim analyses**

No interim analysis is planned for this study.

## 12 Deviations from protocol analysis

For the primary endpoint, subgroup analysis was added (Section 9.2.2 and 9.4.1). In the tolerability analyses section (see Section 9.3.4), the analysis for binary tolerability question was clarified. Furthermore, the analysis of additional efficacy and safety endpoints were specified in Sections 9.4 and 10.5, respectively.

In this amendment the markedly abnormal vital signs summary table that was specified in the protocol has been removed.

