9.8.4 Other Safety Variables

9.8.4.1 Vital Signs

Each vital sign will be summarized by treatment group and scheduled time point using descriptive statistics: sample size, mean, median, standard deviation, minimum, and maximum values. In addition changes from pre-treatment will be summarized in the same way.

The incidence of clinically significant changes in vital signs will be summarized separately by treatment group and scheduled time point.

The incidence of markedly abnormal changes in vital sign values will be summarized by treatment group.

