## Change log

Version No.	Effective Date	Reason for the Change / Revision	Supersedes
1	Oct 7, 2016	SAP based on Protocol dated 20 September 2016	None
2	Nov 29, 2017	

• To lower the trigger for imputation based sensitivity analysis for the primary endpoint.

• The Markedly notable analysis tables for laboratory, vital signs and ECG endpoints has been removed.

• More justification for the margin selection has been added in Appendix 5.

• The fluid intake summary was changed to just include information collected in the patient dairy card.

	1 (for the amendment this would be the 1 version)

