### 10.3.3 Data Listings

Data listings will be prepared by treatment group and site for all subjects with any abnormal or markedly abnormal laboratory value at any time-point (including screening, baseline). The pre-specified markedly abnormal criteria are presented in [Appendix 1](#) Appendix 1 .

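### SAP version 2 removes, without a reason, the by-arm incidence of markedly abnormal vital signs that the protocol commits to, so no SAP table counts subjects by arm at the Appendix 1 thresholds

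*SAP*

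**What the plan says.** Protocol 9.8.4.1 (Vital Signs) states: "The incidence of markedly abnormal changes in vital sign values will be summarized by treatment group". This is separate from the investigator-judged clinically significant changes, which the same section also promises by arm.

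SAP Section 12 then says: "In this amendment the markedly abnormal vital signs summary table that was specified in the protocol has been removed". The SAP change log for version 2 shows a wider removal: "The Markedly notable analysis tables for laboratory, vital signs and ECG endpoints has been removed". Neither place gives a reason.

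SAP Appendix 1 keeps the criteria: Table 2 for laboratory tests, Table 3 for vital signs and Table 4 for ECG. The body of the SAP refers to them in three places, all listings:

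- Laboratory (10.3.3): "Data listings will be prepared by treatment group and site for all subjects with any abnormal or markedly abnormal laboratory value at any time-point".
- Vital signs (10.4.1.2): "Data listings will be prepared by site for all subjects with any abnormal or markedly abnormal vital signs value at any time-point".
- ECG (10.4.2.2): "Data listings will be prepared by treatment group and centre for all subjects with any abnormal ECG or markedly abnormal value at any time-point".

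The laboratory and ECG listings name treatment group as an organising variable. The vital-sign listing names only site.

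**The concern.** Evaluating safety through vital signs, ECGs and laboratory values is a stated secondary objective in both documents. With a bowel preparation, the vital-sign question is less whether the average subject shifts than whether a few subjects shift a lot. A mean and SD over about 450 subjects per arm can look alike in the two arms when a handful of subjects differ. A minimum or maximum shows the single most extreme value, not how many subjects are near it.

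A count at fixed thresholds addresses this directly and does not depend on the investigator's judgement. The protocol chose that output for vital signs. If the SAP is followed as written, a reader of the report who wants the number of subjects per arm with marked hypotension or tachycardia must assemble it by hand from a listing organised by site.

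**Working it through.** No figure in the plan needs reproducing. The check sets the protocol commitment beside each by-arm safety output that the SAP keeps, and asks whether that output gives the same count.

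**What the removed table would have counted.** The footnote to Appendix 1 Table 3 requires a treatment value to meet both the criterion value and the change from baseline:

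- Systolic pressure: at least 180 mmHg with a rise of at least 20, or at most 90 with a fall of at least 20.
- Diastolic pressure: at least 105 mmHg with a rise of at least 15, or at most 50 with a fall of at least 15.
- Pulse: at least 120 bpm with a rise of at least 15, or at most 50 with a fall of at least 15.
- Body weight: a change of at least 7% in either direction, with no criterion value.
- Body temperature is also listed, but it is not among the planned measurements.

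Four measured variables in two directions make 4 × 2 = 8 counts per arm.

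**Remaining by-arm output.**

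1. *Orthostatic counts (SAP 10.4.1).* These count, by visit and arm, subjects with a supine-to-standing systolic fall of at least 20 mmHg, a diastolic fall of at least 10, or a pulse rise of at least 30 bpm accompanied by a pressure drop. The comparison is within a visit, not with baseline. Take a subject whose baseline systolic pressure is at least 105 mmHg and whose post-dose supine and standing values are both 85. The value is at most 90 and the fall is at least 105 − 85 = 20, so Table 3 is met. The supine-to-standing change is 85 − 85 = 0, so the systolic orthostatic cut-off is not. Conversely, a 20 mmHg drop on standing from any supine value above 110 leaves a standing value above 110 − 20 = 90. That is counted as orthostatic but does not meet the Table 3 low criterion. Neither count contains the other.
2. *Vital-sign summaries (SAP 10.4.1.1).* Mean, SD, median, minimum and maximum. There is no count at any threshold.
3. *Laboratory shift tables (SAP 10.3.2).* Number and percentage by arm moving across the reference range, baseline against the worst in-treatment value. Low means anything below the lower limit, so sodium just under range and sodium of 128 mmol/L are counted alike, although Table 2 sets the marked threshold at 130 or below. A subject already Low at baseline who falls further is not a shift.
4. *ECG (SAP 10.4.2 and 10.4.2.1).* By-arm counts of the investigator's overall category, and descriptive statistics for PR, QRS and QTc. There is no by-arm count at the Table 4 QTc thresholds (450, 480 or 500 msec, or rises of 30 or 60 msec).
5. *Adverse-event tables (SAP 10.2).* These include laboratory, vital-sign and examination findings that the investigator considers clinically significant (Protocol 7.2.3 and 8.1). They do not apply fixed thresholds.

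**The judgement-based companion table.** Protocol 9.8.3 and 9.8.4.1 also promise by-arm incidence of clinically significant laboratory and vital-sign changes, and SAP 2.2 keeps this as a secondary endpoint. SAP 10.3 and 10.4.1 describe no such table, and Section 12 does not mention its absence. For vital signs, then, neither incidence table promised by the protocol is described in the SAP text.

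**Which variables can be counted.** Protocol 7.2.1 and 7.2.2 provide weight, blood pressure and pulse. The chemistry panel in Protocol 7.2.3 does not include LDH, phosphorus, uric acid or cholesterol, all of which appear in Table 2. It does include magnesium, for which Table 2 has no criterion.

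**The case against.** The strongest reply is that the change is declared in the section meant for departures from the protocol, that safety is descriptive only, and that much by-arm safety output remains. Most of this is true, and it limits the point.

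- A reader might infer that extreme blood pressure, pulse, QTc and electrolyte values are never counted by arm. The documents do not support that. Orthostatic changes, out-of-range laboratory values and ECG categories are all tabulated by treatment, and findings judged clinically significant reach the adverse-event tables. What is missing is a count at the Appendix 1 thresholds.
- A reader might infer that the protocol promised such tables for laboratory and ECG data too. It did not: Protocol 9.8.3 and 9.8.4.2 refer to clinically significant changes, and only 9.8.4.1 uses the markedly abnormal wording. Removing the other two tables departs from SAP version 1, not from the protocol.
- A reader might infer from the version 2 date, 29 November 2017, that accumulating data prompted the removal. Nothing in the documents shows this. The fourth quarter of 2017 was only the anticipated time of the last visit, and the protocol does not say what form the Safety Review Committee outputs took or who saw them.
- The vital-sign listing covers screening and baseline, but Table 3 requires a treatment value and a change from baseline. Pre-dose rows can therefore be abnormal, not markedly abnormal. Organising by site does not prove that treatment is missing from the listing, and the table and listing shells are a separate document that could not be checked.

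What the reply does not answer is why the table was dropped. Declaring a departure does not justify it, and the remaining outputs do not yield the promised count.

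**Conclusion.** The point holds for vital signs. The protocol commits to a by-arm incidence at pre-specified thresholds, the SAP removes it without a reason, and no other table in the SAP text supplies it. For QTc and laboratory values, the absence of by-arm threshold counts is a weakness of the SAP rather than a breach of the protocol.

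The consequence is limited to descriptive safety reporting on a secondary objective. Primary and secondary efficacy conclusions are unaffected. The documents give no event rates or standard deviations for these measures, so no numerical effect is claimed, and the point does not need one. It rests on the SAP text as written and assumes that the separate shells do not reinstate the table.

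**What to change.** 1. Delete the removal sentence in SAP Section 12 and correct the change log to match.
2. In SAP 10.4.1.1, restore a descriptive table giving the number and percentage of safety-set subjects, by actual treatment, with any post-dose value meeting Appendix 1 Table 3. Limit it to systolic pressure, diastolic pressure, pulse and body weight. Use as denominator the subjects with both a baseline and a post-dose value, and state whether supine, standing or either reading counts. Make no hypothesis tests.
3. In SAP 10.4.1.2, add treatment group to the vital-sign listing.
4. As a recommendation beyond the protocol's commitment, give the same by-arm counts for QTc (Table 4, with both the Bazett and Fridericia corrections) and for those Table 2 laboratory variables that the trial measures. Note in the SAP that Table 2 has no magnesium criterion, so these counts would not cover marked magnesium values.

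If the sponsor prefers to leave the table out, Section 12 should at least give the reason.

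The restored tables use data already collected and criteria already in Appendix 1, so no new visits or measurements are needed. The cost is some SAP wording, some programming, and a slightly longer safety output in which some counts will be small.

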## 14 Tables, Listings and Figures

The document with tables, figures and listings (TLF) shells presented in a separate document.

---

## Appendix 1     Markedly Abnormal Laboratory Safety Values, Vital Signs and ECGs

**Table 2: Markedly abnormal Criteria for Laboratory Tests**

Variable	Units	Markedly abnormal Criteria	
		Low	High
Haematology			
Haemoglobin	g/L	$\leq 115$	Not applicable
Haematocrit	Ratio	$\leq 0.37$	$\geq 0.56$
Total WBC	$10^9/L$	$\leq 2.8$	$\geq 16.0$
Eosinophils	%	Not applicable	$\geq 10$
Neutrophils	%	$\leq 15$	$\geq 90$
Lymphocytes	%	$\leq 10$	$\geq 80$
Monocytes	%	Not applicable	$\geq 20$
Basophils	%	Not applicable	$\geq 5$
Bands	%	Not applicable	$\geq 20$
Platelets	$10^9/L$	$\leq 75$	$\geq 700$
Total RBC	$10^{12}/L$	$\leq 3.5$	Not applicable
Clinical Chemistry			
AST	IU/L	Not applicable	$> 3 \times \text{ULN}$
ALT	IU/L	Not applicable	$> 3 \times \text{ULN}$
Alkaline phosphatase	IU/L	Not applicable	$> 3 \times \text{ULN}$ and 25% increase from baseline
GGT	IU/L	Not applicable	$> 3 \times \text{ULN}$
LDH	IU/L	Not applicable	$> 3 \times \text{ULN}$
Total bilirubin	$\mu\text{mol}/L$	Not applicable	$\geq 1.5 \times \text{ULN}$
Urea nitrogen	mmol/L	Not applicable	$\geq 10.7$
Creatinine	$\mu\text{mol}/L$	Not applicable	$\geq 177$
Total protein	g/L	$\leq 45$	$\geq 90$
Albumin	g/L	$\leq 25$	$\geq 65$
Sodium	mmol/L	$\leq 130$	$\geq 155$
Potassium	mmol/L	$\leq 3.0$	$\geq 5.8$
Chloride	mmol/L	$\leq 90$	$\geq 115$
Phosphorus	mmol/L	$\leq 0.5$	$\geq 1.9$
Calcium	mmol/L	$\leq 1.8$	$\geq 3.9$
Uric acid	mmol/L	Not applicable	$\geq 0.62$
Glucose	mmol/L	$\leq 2.8$	$\geq 10$
Total cholesterol	mmol/L	Not applicable	$\geq 8.0$
Urinalysis: Quantitative			
pH	None	$\leq 4$	Not applicable
Specific gravity	None	$\leq 1.005$	Not applicable
Urinalysis: Dipstick Chemistries			
Glucose	0 - 4+	Not applicable	Increase of 2 or more units from baseline

Variable	Units	Markedly abnormal Criteria	
		Low	High
Casts		Not applicable	Increase of 2 or more units from baseline
Protein	0 - 4+	Not applicable	Increase of 2 or more units from baseline
Ketones	0 - 4+	Not applicable	Increase of 2 or more units from baseline
Blood (Hgb)	0 - 4+	Not applicable	Increase of 2 or more units from baseline
Urinalysis: Microscopic Variables			
RBC	no./hpf	Not applicable	$\geq 10$
WBC	no./hpf	Not applicable	$\geq 20$
Casts	no./hpf	Not applicable	Neg at baseline to positive on-treatment
Bacteria	no./hpf	Not applicable	Neg at baseline to positive on-treatment
Cells	no./hpf	Not applicable	Neg at baseline to positive on-treatment
Crystals	no./hpf	Not applicable	Neg at baseline to positive on-treatment

**Table 3: Markedly abnormal Criteria for Vital Signs\***

Variable	Criterion Value	Change from Baseline
Systolic blood pressure	$\geq 180$ mmHg $\leq 90$ mmHg	Increase of $\geq 20$ mmHg Decrease of $\geq 20$ mmHg
Diastolic blood pressure	$\geq 105$ mmHg $\leq 50$ mmHg	Increase of $\geq 15$ mmHg Decrease of $\geq 15$ mmHg
Pulse rate	$\geq 120$ bpm $\leq 50$ bpm	Increase of $\geq 15$ bpm Decrease of $\geq 15$ bpm
Body weight	None	Increase of $\geq 7\%$ Decrease of $\geq 7\%$
Body temperature	$\geq 38.3^{\circ}\text{C}$	Increase to $\geq 39.4^{\circ}\text{C}$

\* To be identified as markedly abnormal, a treatment value must meet the criterion value and also the specified change from baseline.

**Table 4: Abnormal Criteria for Quantitative ECG Data**

Variable	Baseline	Abnormal Treatment-Emergent Value
ECG heart rate	Normal	$\leq 50$ bpm and decrease from baseline of $\geq 15$ bpm $\geq 120$ bpm and increase from baseline of $\geq 15$ bpm
Duration of PR interval	Normal	$\geq 220$ msec
Duration of QRS interval	Normal	$\geq 120$ msec
Duration of QTc interval	Normal	$\geq 450$ msec
Duration of QTc interval	Normal	$\geq 480$ msec
Duration of QTc interval	Normal	$\geq 500$ msec
Duration of QTc interval*	Not applicable	Increase from baseline of $\geq 30$ msec
Duration of QTc interval	Not applicable	Increase from baseline of $\geq 60$ msec

\* QTc will be calculated both using Bazett's and Fridericia's correction formulae.

## Appendix 2 Statistical and programming details

### Cochran-Mantel-Haenszel method for computing proportion differences adjusting for stratification factor ([11])

- $p_{ij}$  is the portion of success for treatment  $i$  ( $i=1, 2$ ) and site  $j$  ( $j=1, \dots, s$ )
- $d_j = p_{1j} - p_{2j}$  is the  $j$ th site treatment difference
- $w_j = \frac{\left( \frac{n_{1j}n_{2j}}{n_{1j} + n_{2j}} \right)}{\sum_{j=1}^s \left( \frac{n_{1j}n_{2j}}{n_{1j} + n_{2j}} \right)}$

The Cocharan-Mantel-Haenszel confidence interval is as follows:

$$\sum_{j=1}^s w_j d_j \pm z_{\alpha/2} \sqrt{\sum_{j=1}^s w_j^2 \left( \frac{p_{1j}(1-p_{1j})}{n_{1j}} + \frac{p_{2j}(1-p_{2j})}{n_{2j}} \right)}$$

### SAS code for generating multiple imputed data using *proc mi* procedure ([13])

If the primary endpoint (overall colon cleansing based on Modified Aronchick Scale) is missing for a mITT patient and the assessment is not available due to other than tolerability of the IMP the following SAS code can be used to generate 20 imputed data sets.

```
proc mi seed=xxx out=xxxx n impute=20;
class outcome trt site;
monotone logistic(outcome = trt site);
var trt site outcome;
run;
```

Where  $trt$  represents treatment group and  $site$  represents the patient site.

Once the 20 imputed data sets are generated, for each imputed data the above formula can be used to derive the stratified difference and associated variance i.e.,

Estimated difference:  $\hat{Q} = \sum_{j=1}^s w_j d_j$

Associated Variance:  $\hat{U} = \sum_{j=1}^s w_j^2 \left( \frac{p_{1j}(1-p_{1j})}{n_{1j}} + \frac{p_{2j}(1-p_{2j})}{n_{2j}} \right)$

Let  $\widehat{Q}_j$  and  $\widehat{U}_j$  be the point estimate and associated variance for the  $j$ th imputed data set ( $j=1, \dots, k$ ). Then the point estimate pooling over the imputed data sets would be as follows:

$$\bar{Q} = \frac{1}{k} \sum_{j=1}^k \widehat{Q}_j$$

The within-imputation variance is given by

$$\bar{U} = \frac{1}{k} \sum_{j=1}^k \widehat{U}_j$$

And the between-imputation variance is given by

$$B = \frac{1}{k-1} \sum_{j=1}^k (\widehat{Q}_j - \bar{Q})$$

Finally, the total variance associated with  $\bar{Q}$  is as follows:

$$T = \bar{U} + \left(1 + \frac{1}{k}\right)B$$

Then

$$(Q - \bar{Q})T^{-1/2} \sim T\text{-distribution with } v \text{ degrees of freedom}$$

$$v = (k-1)[1 + \bar{U}/((1+k^{-1})B)]^2$$

[figure not shown]
Where  $Q$  is the population parameter.

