3.2 Planned Number of Trial Sites and Subjects

The study will be conducted at approximately 10-15 sites in the US and Canada. A sufficient number of subjects will be screened to ensure enrollment of 900 randomized subjects (approximately 450 subjects per treatment group).

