The NI analysis will also be conducted for the per-protocol (PP) population as a sensitivity analysis. An additional sensitivity analysis may be performed, where a multiple imputation method will be applied to impute for subjects with missing colonoscopy assessment for reasons other than drug tolerability and for patients where water insufflation was used. Details of such analysis will be described in the analysis plan.

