#### 9.2.1 Primary Variable(s) Analysis

For primary analysis what is of interest is the assessment of the difference in responder rates in overall colon cleansing between NaP/MC Oral Solution and PREPOPIK®. A subject is considered to be a “responder” if overall colon cleansing is classified as either “excellent” or “good” by the blinded endoscopist using the Modified Aronchick Scale (see [Appendix 3](#) ). The NI margin for the difference between treatments (NaP/MC Oral Solution minus PREPOPIK®) will be -8% (absolute). The NI hypothesis to be tested for the primary endpoint will be:

$$H_0: \pi_{\text{NaP/MC Oral Solution}} - \pi_{\text{PREPOPIK}^{\circledR}} \leq -8\%$$

against the alternative

$$H_1: \pi_{\text{NaP/MC Oral Solution}} - \pi_{\text{PREPOPIK}^{\circledR}} > -8\%,$$

where  $\pi_{\text{NaP/MC Oral Solution}}$  and  $\pi_{\text{PREPOPIK}^{\circledR}}$  denote the true percentage of subjects classified as responders (i.e., excellent and good according to the Modified Aronchick Scale (see [Appendix 3](#) )) among subjects treated with NaP/MC Oral Solution or PREPOPIK®, respectively, for colon cleansing in preparation for colonoscopy.

The null hypothesis ( $H_0$ ) will be tested against the alternative by constructing a 2-sided 95% confidence interval for the difference in responder rates. The primary analysis will be stratified by the stratification factor, site, by using the Mantel-Haenszel method to combine results across sites. In brief, this corresponds to deriving a weighted average across sites where the weight depends on the number of observations in each treatment group in each stratum (see [Appendix 2](#) for more details). Subjects who do not have an excellent or good rating according to the Modified Aronchick Scale (see [Appendix 3](#)) for any reason will be considered treatment failures (i.e., not a responder). Hence, treated patients that did not complete the colonoscopy assessment will be classified as non-responders. If the lower limit of the 95% confidence interval is greater than the margin (-8%), the null hypothesis will be rejected and it will be claimed that NaP/MC Oral Solution is non-inferior to PREPOPIK® with respect to colon cleansing in preparation for colonoscopy.

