## 9.2.2 Sensitivity Analyses

As a sensitivity analysis, the NI analysis in [section 9.2.1](#) will be repeated using the per-protocol population.

For the primary analysis, if a patient does not have efficacy assessment (colonoscopy), it is considered to be a treatment failure. There are two main reasons for applying such method of imputations. First, the number of patients missing efficacy assessment is expected to be very low. In the two pivotal Ferring studies (FE2009-01 and FE2009-02), the number of patients that were treated but did not have colonoscopy assessment were less than 1%. Furthermore, if the reason for not having efficacy assessment is related to tolerability then these can also be considered as treatment failures and treating such missing values as failures is appropriate. However, in this study, if the number of treated patients that do not have efficacy assessment for reasons other than tolerability is  $\geq 0.5\%$ , there will be a sensitivity analysis, where, a multiple imputation method will be applied to impute for such missing colonoscopy assessment. Details of the multiple imputation method to be applied is found in [Appendix 2](#)

The patients that do not have colonoscopy results for other than tolerability issues will be identified using the question “was colonoscopy performed at this visit?” on the colonoscopy & assessment eCRF page. Using the “specify” responses to this question, prior to data base lock, the clinical team will review and categorize the reasons for not performing or completing colonoscopy. One of the classification categories will be “tolerability”. If there are  $\geq 0.5\%$  patients that did not have colonoscopy performed or completed for reasons other than “tolerability” a sensitivity analysis will be performed by applying multiple imputation method to impute for such missing assessments.

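### The between-imputation variance in SAP Appendix 2 has no square, so it is zero for any data; only the triggered multiple-imputation sensitivity analysis is affected

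*SAP*

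**What the plan says.** SAP section 9.2.2 provides for a multiple-imputation sensitivity analysis of the primary endpoint. It is to be run if at least 0.5% of treated patients have no colonoscopy assessment for reasons other than tolerability. For the method the section points elsewhere: "Details of the multiple imputation method to be applied is found in" Appendix 2. Protocol section 9.6.2 lists the same analysis as optional ("An additional sensitivity analysis may be performed, where a multiple imputation method will be applied") and leaves the details to the analysis plan.

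Appendix 2 says that "the following SAS code can be used to generate 20 imputed data sets", then sets out the pooling by hand:

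- The pooled estimate, introduced by "Then the point estimate pooling over the imputed data sets would be as follows", is Q̄ = (1/k) Σ Q_j.
- The within-imputation variance is Ū = (1/k) Σ U_j.
- Under "And the between-imputation variance is given by" stands B = (1/(k−1)) Σ (Q_j − Q̄), with no exponent after the bracket.
- The total variance is T = Ū + (1 + 1/k)B.
- The degrees of freedom are v = (k−1)[1 + Ū/((1 + 1/k)B)]².

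The primary analysis in SAP section 9.2.1 does not use these formulas. There, "treated patients that did not complete the colonoscopy assessment will be classified as non-responders", and the interval is the stratified one given at the start of Appendix 2.

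**The concern.** A between-imputation variance should measure the spread of the estimates across imputed data sets. The expression given is a sum of signed deviations from their own mean, which always cancels. Followed literally, it removes from T the component that multiple imputation exists to supply, and it leaves the reference distribution undefined because B is in the denominator of v.

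Appendix 2 is the only pooling rule in the documents, and once the trigger is met the analysis is required. The direction is non-conservative, since an interval that is too narrow makes non-inferiority slightly easier to support. At stake is the validity of one prespecified sensitivity interval, and whether someone reproducing the analysis from the text would obtain the sponsor's result.

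**Working it through.** **1. Algebra.** Since Q̄ = (1/k) Σ Q_j, we have Σ (Q_j − Q̄) = kQ̄ − kQ̄ = 0. Hence B = 0 for any data, T = Ū, and v contains Ū/0. In floating-point arithmetic the largest |B| seen in simulation was 2.2e-17, which is rounding only. With Ū near 5.8e-4, such a residue gives v ≈ 19 × [5.8e-4 / (1.05 × 2.2e-17)]² ≈ 10^28, in effect a normal reference. An exact zero gives a division error.

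**2. Trigger.** 0.005 × 900 = 4.5. Four patients are 4/900 = 0.44% and five are 5/900 = 0.56%, so the analysis starts at 5 if all 900 are treated. SAP section 9.2.2 cites fewer than 1% of treated patients without an assessment in the two earlier studies; 1% of 900 is 9.

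**3. Baseline precision.** The SAP gives no number for the pooled interval, so its sample size serves as a check on the inputs. With 84% in both arms, margin 8 points, one-sided 0.025 and 90% power, the standard formula needs 442 per arm. At the planned 450 the power is 90.5%, which agrees with the SAP. The unstratified standard error is √(2 × 0.84 × 0.16 / 450) = 0.02444, a half-width of 1.96 × 2.444 = 4.79 points. With 12 equal sites there are 900/24 = 37.5 patients per arm and site. Using observed proportions in each cell lowers the variance by the factor 1 − 1/37.5 = 0.973, so the expected half-width is 4.79 × √0.973 ≈ 4.73.

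**4. Size of the error.** Assumptions for the simulation: 900 treated, 84% response in both arms, outcomes missing at random, 12 equal sites (the protocol says "The study will be conducted at approximately 10-15 sites in the US and Canada"), 20 logistic imputations on treatment and site with parameter draws, the Appendix 2 stratified estimate and variance, and 300 trials per row. The column without the square uses T = Ū and a normal quantile.

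| Missing | Half-width, no square | Half-width, squared | Shortfall (points) |
|---|---|---|---|
| 5 (0.56%) | 4.722 | 4.737 | 0.014 (0.015 from the rounded columns) |
| 9 (1%) | 4.728 | 4.753 | 0.025 |
| 18 (2%) | 4.740 | 4.794 | 0.05 |
| 45 (5%) | 4.726 | 4.863 | 0.14 |

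Layouts with 10 or 15 equal sites, or 12 unequal ones, give practically the same shortfalls. Over 10 to 15 sites the corrected standard error is larger by 0.3%, 0.5–0.6%, 1.1% and 2.8–3.0% in the four rows.

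Hand check for 5 missing, using mean values from a separate run: Ū = 5.82e-4 and squared B = 3.5e-6. Then T = 5.82e-4 + 1.05 × 3.5e-6 = 5.857e-4. Half-widths are 1.96 × √5.82e-4 = 4.73 and 1.96 × √5.857e-4 = 4.74 points.

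With the squared B, the median v is above 500,000 for 5 missing and 6,400–7,200 for 45, so the t quantile is about 1.96. Once B is corrected, v has no practical effect.

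**5. Effect on the non-inferiority reading of this analysis.** The true difference was set at −3.3 points so that the lower limit falls near −8. In 2,000 trials per row, the reading changed in 0.20% (4 trials) with 5 missing, 0.40% (8) with 9 and 2.05% (41) with 45. An approximation agrees: the density of the estimate at its centre is 0.399/2.4 = 0.166 per point, and 0.166 × 0.014 = 0.23% and 0.166 × 0.025 = 0.42%.

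**The case against.** - **It may be a reading loss.** One superscript is missing from a formula read out of a PDF, and losing a single exponent is possible. Against that, the exponents on the weights, on T and on the bracket in v all survive in the same appendix. An omission in the SAP is more likely but not proven, so the source must be checked.
- **The intended rule is obvious.** B is called a variance, is divided by k−1 and is built on deviations from the mean; only the squared form fits. An experienced programmer would probably use it. That is a fair reason to expect little harm, but a prespecified formula should not depend on a silent departure from it.
- **The formula cannot strictly be run.** The shortfalls above assume that B is taken as zero and a normal quantile is used, a fallback the SAP does not state. They describe the limiting case, which is also what a rounding residue would produce.
- **The trigger may not be met.** The earlier-study figure of under 1% covers all reasons, while the trigger counts only those unrelated to tolerability, and the documents give no split. It is compatible with 5 or more such patients but does not show that there will be.
- **The size is negligible.** This stands. At 5 to 9 missing, the change is of the order of 0.01–0.03 points. The percentages in step 5 put the truth where a change is most likely, and the two smallest rest on 4 and 8 events (exact 95% intervals roughly 0.05–0.5% and 0.2–0.8%). Under the SAP's equal-rates assumption the normal approximation gives about 0.09% and 0.16%. The 5% row lies well outside the missingness the SAP expects.

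**Conclusion.** The point holds as a minor error. On the text available, the stated B is identically zero, imputation uncertainty drops out of T, and v is undefined. The consequence is confined to the multiple-imputation sensitivity analysis; the per-protocol analysis, the sample size and all the formal tests are untouched. At the missingness the SAP anticipates, the half-width of about 4.7 points would be short by roughly 0.01 to 0.03 points, in the non-conservative direction. This size rests on 900 treated, 84% response in both arms, missingness at random and 10 to 15 sites. Confidence is medium, only because the source PDF has not been inspected for the exponent.

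**What to change.** Check the formula in the source PDF. If the square is absent there too, replace it with B = (1/(k−1)) Σ (Q_j − Q̄)², or state that the 20 estimates and variances are pooled with PROC MIANALYZE. T and v need no change.

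The cost is one exponent in Appendix 2. The sensitivity interval widens by about 0.01–0.03 points on each side at 0.5–1% missing. Nothing changes in the primary analysis, the sample size or data collection.
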